8.2.1.2. Drug-Related Adverse Events

Drug-related summary tables will be produced for AEs related to blinded study medication (albiglutide/placebo) only. No summaries will be produced for AEs related to insulin. This definition applies throughout the AE section, when drug-related events are mentioned. See Section 11.5.3 for further details.

If a relationship to the study drug is missing or unknown after the start of treatment it will be assumed, for the purpose of analyses, to be drug-related (to blinded study medication).

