8.2.1.3. Adverse Events by Maximum Intensity

Subjects who experience the same event several times, with different intensity, will only be counted once according to the maximum intensity experienced (for that therapeutic phase). AEs with missing intensity will be considered to be severe for the purposes of summarisation.

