
 Subjects reported hypoglycaemic events will be classified as defined by the ADA Workgroup on Hypoglycaemia [Sequist, 2013]. Severe Hypoglycaemia: an event requiring assistance of another person to actively administer carbohydrates, glucagon, or take other corrective actions. Plasma glucose concentrations may not be available during an event, but neurological recovery following the return of plasma glucose to normal is considered sufficient evidence that the event was induced by a low plasma glucose concentration Documented Symptomatic Hypoglycaemia: an event during which typical symptoms of hypoglycaemia are accompanied by a measured plasma glucose concentration ≤ 70 mg/dL (≤ 3.9 mmol/L) Asymptomatic Hypoglycaemia: an event not accompanied by typical symptoms of hypoglycaemia but with a measured plasma glucose concentration ≤ 70 mg/dL (≤ 3.9 mmol/L) Probable Symptomatic Hypoglycaemia: an event during which symptoms typical of hypoglycaemia are not accompanied by a plasma glucose determination but that was presumably caused by a plasma glucose concentration ≤ 70 mg/dL (≤ 3.9 mmol/L) Pseudo Hypoglycaemia: an event during which the person with diabetes reports any of the typical symptoms of hypoglycaemia with a measured plasma glucose concentration > 70 mg/dL (> 3.9 mmol/L) but approaching that level Events will be classified into ADA categories based on the following questions: 
 1. 'Did you require someone else's help to get the treatment needed?' (Yes/No) 2. 'Any symptoms?' (Yes/No) 	

Subject-Reported Hypoglycaemic Events

- 3. 'Lowest plasma glucose reading at the time of the event' (numeric value/Not Done)
- Note: Glucose readings from subject-reported hypoglycaemic events initial reported in the eDiary are identified in the laboratory dataset by VISIT='HYPOGLYCAEMIC EVENT'.
- Glucose will be presented in mmol/L. A glucose value reported in mg/dL will be converted to mmol/L by multiplying the value by 0.05551.

The ADA categories will be assigned based upon the questions above as follows:

- Severe: Required assistance (Q1) = Yes
- Documented Symptomatic: Symptoms (Q2) = Yes and Glucose reading (Q3) = ≤ 3.9 mmol/L
- Asymptomatic: Symptoms (Q2) = No or missing and Glucose reading (Q3) = ≤ 3.9 mmol/L
- Probable Symptomatic: Symptoms (Q2) = Yes and Glucose reading (Q3) = Not done
- Pseudo: Symptoms (Q2) = Yes and Glucose reading (Q3) = > 3.9 mmol/L
- i.e.,

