ADA classification	Required Assistance	Symptoms	Glucose Reading (mmol/L)
Severe	Yes	Any*	Any*
Documented Symptomatic	No or missing	Yes	$0 < \text{glucose} \leq 3.9$
Asymptomatic	No or missing	No or missing	$0 < \text{glucose} \leq 3.9$
Probable Symptomatic	No or missing	Yes	Glucose = 0 or missing
Pseudo	No or missing	Yes	Glucose > 3.9

* includes missing values

- A subject reported event that does not meet any of the above criteria will not be counted as a hypoglycaemic event (any events will be flagged to the study team for review).
- Only hypoglycaemic events that subjects record in the glucose meter will be included in the summaries of subject-reported hypoglycaemic events. Glucose readings reported, for example, as part of standard laboratory testing or the 7-point glucose profile will not be included.
- Each event will be assigned to one ADA category, but a subject may report events from multiple ADA categories. A subject will appear in all ADA categories they experience.

Daytime/Nocturnal Events

- Subjects report the start date/time of a hypoglycaemia event. The start time of event will be used to classify the event as daytime or nocturnal.
- Daytime Hypoglycaemia: an event with an onset time between 06:00h and 00:00h (inclusive). i.e., in SAS time format (secs): start time = 0 or start time > 21541
- Nocturnal Hypoglycaemia: an event with an onset time between 00:01h and 05:59h (inclusive). i.e., in SAS time format (secs): $0 < \text{start time} \leq 21540$
- Events with a missing start time will be classified as Daytime events

Time periods (3 monthly intervals)

 Events will be assigned to time periods will are defined using the following categories: Baseline to \leqWeek 12: Study day 1 to \leq84 $>$Week 12 to \leqWeek 24: Study day 85 to \leq168 $>$Week 24 to \leqWeek 36: Study day 169 to \leq252 $>$Week 36 to \leqWeek 52: Study day 253 to \leq364 $>$Week 52 to \leqWeek 64: Study day 365 to \leq448
Time periods (2 weekly intervals)

 A summary of events by 2 weekly time periods will also be produced. E.g., Day 1 to Day 14; Day 15 to Day 28; etc.
Denominators for time period summaries

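### Hypoglycaemic events with missing diary answers can never be counted as nocturnal or severe, so those counts can only equal or fall below the truth

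*SAP*

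**What the plan says.** Three rules in SAP section 11.5.3 (Subject-Reported Hypoglycaemic Events) decide what happens when a diary item is blank.

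- **Onset time.** Nocturnal means a recorded onset from 00:01 to 05:59. For a blank time: "Events with a missing start time will be classified as Daytime events".
- **Symptoms.** "Asymptomatic: Symptoms (Q2) = No or missing", provided the glucose reading is at or below 3.9 mmol/L and assistance was not answered Yes.
- **Assistance.** "Severe: Required assistance (Q1) = Yes". Each of the four other rows of the classification table accepts either No or a blank.

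For events that match no row: "A subject reported event that does not meet any of the above criteria will not be counted as a hypoglycaemic event". These events are passed to the study team for review.

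For adverse events the SAP goes the other way. Section 8.2.1.3: "AEs with missing intensity will be considered to be severe". Section 8.2.1.2: "If a relationship to the study drug is missing or unknown after the start of treatment it will be assumed" to be drug-related. Section 11.6.2.1 places an AE with no start date in the on-therapy phase and calls this the worst case.

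Sections 8.1.1.1 and 8.2.1.7.3 allow optional exploratory work on hypoglycaemia, depending on how much is missing. They specify no unknown category, no count of missing answers and no sensitivity table.

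**The concern.** Protocol section 1.3.1 lists hypoglycaemia as an identified risk that rises when albiglutide is combined with insulin, and every subject here has insulin as background therapy. Incidence by ADA category and by day or night are named safety endpoints (SAP section 2.2), reported in Tables 3.22 and 3.24. Hypoglycaemia enters the AE tables only when it meets the SAE definition (SAP section 8.2.1.1), so the worst-case AE rules do not protect non-serious events.

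Under section 11.5.3 a blank answer is not shown as unknown. It is given a definite value, and that value is never nocturnal and never severe. A reader of the tables cannot tell a confirmed daytime event from one with no time, or a confirmed unassisted event from one where the question was left blank. The review flag covers only events that fit no row; a blank that does fit a row is recoded without a flag. What is at stake is the absolute incidence of these categories.

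**Working it through.** The plan states no figure to reproduce. The check has two parts: run the rules over every answer pattern, then apply assumed missing rates.

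**1. The rules.** Inputs from SAP section 11.5.3: assistance (Yes, No, missing) × symptoms (Yes, No, missing) × glucose (≤3.9, >3.9, missing) = 27 patterns.

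| Patterns | Number | Where they go |
|---|---|---|
| Assistance missing | 9 | Severe 0; documented symptomatic 1; probable symptomatic 1; pseudo 1; asymptomatic 2; not counted 4 |
| Symptoms missing, assistance not Yes | 6 | any symptomatic category 0; asymptomatic 2; not counted 4 |
| Onset time missing | any | nocturnal 0 |

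The four uncounted patterns in the second row have glucose above 3.9 or missing. The four in the first row have that same glucose condition and symptoms not Yes.

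If the recorded answers are correct, nothing can enter the severe or nocturnal cell wrongly, and events can only be lost from it.

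**2. Effect on the pooled secondary endpoint.** SAP section 11.5.4 pools severe, documented symptomatic and asymptomatic events as significant hypoglycaemia. With a reading at or below 3.9 the event stays in the pool whatever else is blank. A truly severe event with assistance missing and no low reading leaves it: it becomes probable symptomatic (symptoms Yes, no glucose), pseudo (symptoms Yes, glucose above 3.9) or uncounted (symptoms No or missing). Section 11.5.3 itself notes that glucose may be unavailable during a severe event.

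**3. Size under assumed missing rates.** Assumptions, none from the documents: a fraction m of answers is missing independently for each item; glucose is always recorded and ≤3.9; all severe events are symptomatic; the true mix is 2% severe, 58% documented symptomatic and 40% asymptomatic; 25% of events are nocturnal.

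- Severe = 0.02 × (1 − m)
- Documented symptomatic = 0.58 × (1 − m) + 0.02 × m × (1 − m)
- Asymptomatic = 0.40 + 0.58 × m + 0.02 × m²
- Nocturnal = 0.25 × (1 − m)

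| m | Severe | Documented symptomatic | Asymptomatic | Nocturnal |
|---|---|---|---|---|
| 0 | 2.00% | 58.0% | 40.0% | 25.0% |
| 5% | 1.90% | 55.2% | 42.9% | 23.75% |
| 10% | 1.80% | 52.4% | 45.8% | 22.5% |
| 20% | 1.60% | 46.7% | 51.7% | 20.0% |

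The three categories sum to 100% in each row only because glucose was assumed always recorded and low.

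**4. Documented symptomatic is not strictly one-directional.** A severe event with only the assistance answer missing moves into it. With assistance missing at 10% and symptoms complete: 0.58 + 0.02 × 0.10 = 58.2%, a small rise. Symptom missingness outweighs this once it exceeds 0.002 / 0.582 = 0.3%, so a fall is the usual result under this mix.

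**5. Scale in subjects.** At the planned sizes in protocol section 5.2, one subject is 1/51 = 2.0% on albiglutide and 1/17 = 5.9% on placebo. Recoding a subject's only severe event changes the percentage affected by that much.

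**The case against.** The best defence is that the effect may be nil. Events come from an electronic diary with Yes/No questions, and the investigator reviewed them (SAP section 11.5.3). That stands: no missing rate is given, so a reader who infers that these categories *are* understated goes beyond the documents. The review described concerns which events were serious; the SAP does not say that it completes blank answers.

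Second, other outputs limit the harm. Serious events are also in the AE data, events below 3.1 mmol/L are summarised regardless of symptoms (Table 3.23), and a by-subject listing is planned (Listing 55). This stands too. None of these shows how many events in Tables 3.22 and 3.24 were placed by default.

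Third, the summaries are descriptive, and the same rules apply to both arms of a double-blind trial. Equal missingness distorts the contrast little, and the documents do not support a claim that the treatment comparison is biased. Absolute incidence is still affected.

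Fourth, the AE-style worst case is not clearly better here. With the mix above and 5% of assistance answers missing, coding them all as severe gives 0.02 + 0.05 × 0.98 = 6.9%, against 1.9% under the SAP and a true 2%. With 10% of times missing, nocturnal becomes 0.25 + 0.10 × 0.75 = 32.5%, against 22.5% and a true 25%. This stands, and is why the main remedy is disclosure and not the opposite recoding.

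**Conclusion.** The concern holds as a minor point about safety reporting. As written, severe and nocturnal counts can only equal or fall below the truth, and documented symptomatic counts will usually fall. The direction follows from the rules alone, given correct recorded answers. The size rests on a missing rate that the documents do not supply: the relative shortfall in nocturnal events equals the fraction of nocturnal events with no time, and likewise for severe events with no assistance answer. It is zero if nothing is missing.

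Two further inferences should be avoided. One is that only the split between categories changes while totals stay fixed. Events with symptoms missing, glucose above 3.9 or missing, and assistance not Yes are dropped from the total, though flagged, and a severe event with assistance missing and no low reading leaves the significant hypoglycaemia endpoint. The other is that every category errs the same way; documented symptomatic can rise slightly.

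The rules run against the SAP's own handling of missing AE information, and no reason is given for the difference.

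**What to change.** Stop assigning blank answers to daytime, asymptomatic or not severe without disclosure. In Tables 3.22 and 3.24 add separate rows for time unknown, symptoms unknown (glucose ≤3.9 mmol/L) and assistance unknown. Report by arm the number of events in each, and the number not counted because they fit no category. Because the SAP assigns each event to one ADA category, state which unknown row takes precedence when two answers are blank. Events with a reading at or below 3.9 mmol/L should stay in the pooled significant hypoglycaemia endpoint, since the reading alone qualifies them.

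A version that counts unknown time as nocturnal, unknown symptoms as documented symptomatic and unknown assistance as severe may be added as an optional sensitivity table, labelled as an upper bound for the nocturnal and severe counts.

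The cost is a change of SAP wording and a few table rows. Day and night will sum to the total only when the unknown row is included. No new data are needed and the primary analysis is untouched. If little is missing, the new rows will show it.

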
 The protocol specifies 'a test for treatment group-by-time (continuous) interaction in the model (adjusted for baseline value and randomisation strata)' 	
 'a test for treatment group-by-time (continuous) interaction in the model (adjusted for baseline value and age)' 	
 To correct the protocol text, as the randomisation is not stratified in this study. The correct covariate should have been age.

 The protocol specified 'If a laboratory test is repeated because of an apparent error, the repeat test result will be used in place of the original test result. Both the original test result and the repeat test result will be shown in the listings' 	
 This sentence has been deleted. Laboratory data will be summarised by nominal visit, unscheduled values will be included in summaries of worst-case results at any time post 	
 To clarify how programming will handle these laboratory assessments, as repeat laboratory tests will not be included in by-visit summaries.

Protocol	Reporting & Analysis Plan	
Statistical Analysis Plan	Statistical Analysis Plan	Rationale for Changes
	baseline (e.g. results of potential clinical interest, out of normal range).	

 Secondary endpoint: Population estimates of PD parameters (e.g., Emax, EC₅₀), associated inter-subject variability and residual error if permitted by the data 	
 Analysis of this endpoint will not be conducted. 	
 The company is not developing Albiglutide for Type 1 diabetes mellitus so analysis of this endpoint will not be conducted.

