8.2.2.1. Chemistry, Hematology and Urinalysis

Established or generally acknowledged methods, normal ranges, and quality control procedures will be supplied by Q2 Solutions for the study records.

Only data from the central laboratory will be included in the tables, figures and listings. Data from local laboratories will not be included.

Glucose data from the eDiary card will not be included in any laboratory TFLs.

The number of subjects with results relative to the potential clinical importance criteria will be summarised by laboratory test and category (including liver function tests). Data will be summarised by visit, including ‘any on-therapy visit’ and ‘any post-baseline visit’. The criteria for laboratory values of potential clinical importance are detailed in Section 11.7.1.

Urinalysis data with categorical results will be summarised at each assessed timepoint by treatment group, using number and percentage of subjects with each category.

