- [9] All 12-lead ECGs to be performed in triplicate (approx 10 mins apart) and before measurement of vital signs and collection of blood samples for laboratory testing. Subjects to be semi-recumbent for 10 to 15 minutes before ECGs.
- [10] Only diabetic ketoacidosis SAEs, hypoglycaemia SAEs and SAEs thought to be related to study procedures need to be reported during Screening
- [11] See protocol Section 6.4.2 for hypoglycaemia event criteria and reporting requirements. Urine ketostix to be performed regularly according to clinical practice (see protocol Section 5.1.2)
- [12] Fasting is defined as no food or drink (except water) for at least 8 hours before blood draw.
- [13] Anti-GAD, anti-IA2, IAA
- [14] If results are required quickly for eligibility purposes, local labs may be used for the Screening sample only. If local labs are used, a screening sample must also be sent to the central lab.
- [15] Immunogenicity sampling is to be done prior to dosing throughout study
- [16] Haematology to include complete blood count with haemoglobin, other red blood cell indices, white blood cell count differential, and platelet count.
- [17] Clinical chemistry to include: glucose, blood urea nitrogen, creatinine, sodium, potassium, chloride, carbon dioxide, calcium, total protein, albumin, total bilirubin, direct bilirubin, alkaline phosphatase, alanine aminotransferase, aspartate aminotransferase, γ -glutamyltransferase, uric acid, magnesium, phosphorus.
- [18] If abnormal at Week 52
- [19] Urinalysis to include: specific gravity, pH, glucose, protein, blood by dipstick (if warranted, a microscopic evaluation will be completed).
- [20] Blood sample for pharmacogenetics (PGx) can be collected at any time during the study after the PGx informed consent has been obtained and the subject has been randomly assigned to a treatment group.
- [21] 2ml blood sample. Sample at Week 4 and Week 6 to be taken at least 2 days (48 hours) after the most recent dose of study medication and at any time prior to the next scheduled dose. At Week 6 or any subsequent visit where up or down titration of albiglutide/matching albiglutide placebo coincides with PK sampling, the PK sample must be taken prior to titration, such that it is taken no more than 16 hours prior to the subsequent dose. At Week 8 and Week 16, sample to be collected at least 2 days (48 hours) after a dose but not within 4 days of another sample.

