
(timepoint) = null and visit = null [these can be identified in SI.LAB with visit="HYPOGLYCAEMIC EVENT"]
 
 ○ Routine glucose monitoring readings are identified where LBTPTNUM = 150, 160, 170, 180, 190, 200 corresponding to (OTHER, BEFORE MEAL, AFTER MEAL, AFTER MEDICATION, AFTER SPORT, CONTROL) ○ 7 Point glucose monitoring readings are identified where LBTPTNUM = 80, 90, 100, 110, 120, 130, 140 corresponding to (BEFORE BREAKFAST, 2 HRS AFTER BREAKFAST, BEFORE LUNCH, 2 HRS AFTER LUNCH, BEFORE DINNER, 2 HRS AFTER DINNER, AT BEDTIME). Data directly from the eDiary with VISIT = null. Data recorded into the eCRF with VISIT present (not null). ○ 72h CGM data are identified where LBSPEC='INTERSTITIAL FLUID' and LBMETHOD='TRANSDERMAL MONITORING'.
Laboratory Values Below Limits of Quantification and Repeat Testing

 • Laboratory results that are beyond the limits of quantification will have the inequality sign dropped (<, ≤, >, or ≥) and the quantification limit will be used as the numeric result for summarisation.
Potential Clinical Importance (PCI)

 • The categories for PCI criteria are: Low; Normal; High. • Data will be summarised by nominal visit, but will also include 'any on-therapy visit' and 'any post-baseline visit' categories. These 'any visit' categories will also include unscheduled visits. • The data is summarised using a shift table, comparing the baseline category to the worst case post-baseline category at that time-point (note, worst case is applicable for the 'any visit' categories). The percentages are based on the number of subjects in the treatment group with data for the laboratory test post-baseline at that time-point. Subjects with a missing baseline value are to be assumed to have a normal/within range baseline value. • Worst case can be either High or Low. If a subject has both a decrease 'Low' and an increase 'High', then the subject is counted in both the 'Low' and 'High' categories.
Hepatotoxicity

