3.38.	Safety		Summary Characteristics of On-therapy Investigator-Reported Injection Site Reactions by Anti-Albiglutide Antibody Status		SAC [1]
3.39.	Safety	AE1	Summary of On-therapy Investigator-Reported Systemic Allergic Reactions by SOC and PT		SAC [1]
3.40.	Safety		Summary of On-therapy Investigator-Reported Renal Impairment by SOC and PT		SAC [1]
3.41.	Safety		Summary of On-therapy Diabetic Ketoacidosis (DKA) identified by a Customised MedDRA Query by SOC and PT		SAC [1]
3.42.	Safety		Summary of On-therapy Appendicitis identified from a Customised MedDRA Query by SOC and PT		SAC [1]
3.43.	Safety		Summary of On-therapy Malignant Neoplasms identified from a Standard MedDRA Query by SOC and PT		SAC [1]
3.44.	Safety		Summary of On-therapy Liver Events identified from a Customised MedDRA Query by SOC and PT		SAC[1]
Laboratory: Chemistry					
3.45.	Safety	LB1	Summary of Chemistry Changes from Baseline by Visit	ICH E3	SAC [1]
3.46.	Safety	LB17	Summary of Chemistry Shifts from Baseline with Respect to Potential Clinical Importance (PCI) Criteria	ICH E3	SAC [1]

Safety : Tables					
No.	Population	IDSL / TST ID / Example Shell	Title	Programming Notes	Deliverable [Priority]
Laboratory: Hematology					
3.47.	Safety	LB1	Summary of Hematology Changes from Baseline by Visit	ICH E3	SAC [1]
3.48.	Safety	LB17	Summary of Hematology Shifts from Baseline with Respect to Potential Clinical Importance (PCI) Criteria	ICH E3	SAC [1]
Laboratory: Urinalysis					
3.49.	Safety	LB1	Summary of Urinalysis Changes from Baseline by Visit	ICH E3	SAC [1]
3.50.	Safety	UR3	Summary of Urinalysis Categorical Results	IDSL	SAC [1]
Laboratory: Hepatobiliary (Liver)					
3.51.	Safety	LIVER1	Summary of Liver Monitoring/Stopping Event Reporting	IDSL	SAC [1]
3.52.	Safety	LIVER10	Summary of Hepatobiliary Laboratory Abnormalities	IDSL	SAC [1]
ECG					
3.53.	Safety	EG1, GLP113121, Switch	Summary of ECG Findings by Visit	IDSL	SAC [1]
3.54.	Safety	EG2, per vitals/lab templates	Summary of ECG Changes from Baseline by Visit	IDSL	SAC [1]
3.55.	Safety	per vitals/lab templates	Summary of ECG Shifts from Baseline with Respect to Potential Clinical Importance (PCI) Criteria		SAC [1]
3.56.	Safety	CP_EG11, GLP113121, Switch	Summary of QTcB and QTcF ECG Results by Visit and Category	IDSL	SAC [1]

Safety : Tables					
No.	Population	IDSL / TST ID / Example Shell	Title	Programming Notes	Deliverable [Priority]

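### Week 64 haematology, chemistry and urinalysis are scheduled only for subjects abnormal at Week 52, yet the SAP's by-visit laboratory tables do not exempt that visit

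*SAP*

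**What the plan says.** **When the tests are taken.** Protocol Table 3, reproduced in SAP 11.1.1, has one combined haematology/chemistry row and one urinalysis row. In both, the Week 64 cell carries footnote 18: "If abnormal at Week 52". The cells up to Week 52 and the early-withdrawal cell carry no such condition. Neither document defines abnormal here, or says whether the single test or the whole panel is repeated.

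**How they are summarised.**
- SAP 2.1 puts laboratory data by nominal visit, with unscheduled values entering only the worst-case summaries. SAP 11.4.3 keeps unscheduled visits out of most summary tables, but Week 64 is a scheduled visit and so stays in.
- For PCI, SAP 11.5.3 says: "Data will be summarised by nominal visit, but will also include 'any on-therapy visit' and 'any post-baseline visit' categories". The denominator rule follows: "The percentages are based on the number of subjects in the treatment group with data for the laboratory test post-baseline at that time-point".
- SAP 8.2.2.1 repeats the by-visit rule for PCI ("Data will be summarised by visit, including" the two any-visit categories) and summarises urinalysis categories at every assessed time-point.
- The table list in SAP 11.13.7 includes "Summary of Chemistry Changes from Baseline by Visit" (Table 3.45) and "Summary of Hematology Changes from Baseline by Visit" (Table 3.47), the PCI shift tables (3.46, 3.48) and two urinalysis tables (3.49, 3.50). No programming note restricts the visits shown.

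**The concern.** Each rule is ordinary alone; together they produce a misleading row. Up to Week 52 the denominator is roughly everyone still attending. At Week 64 it is whoever was retested because of an earlier abnormal result. These subjects are missing by design, and the design depends on the outcome being summarised.

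A reader going down a column could take a higher Week 64 percentage as an off-drug signal, when the change comes from who was tested. Printing n shows that the row is imprecise. It does not show that everyone in it was preselected.

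The near-identical PCI wording for vital signs does no harm, because Week 64 vital signs are unconditional. Elsewhere the SAP does set denominators with care: by-period hypoglycaemia percentages use the subjects at risk in each period.

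**Working it through.** The plan gives no figure for this point, so there is none to reproduce. The check is of the text, followed by an illustration of size.

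**1. Does any rule remove Week 64?** No. It is a scheduled nominal visit, the tables carry no visit restriction, and no SAP section footnotes the selection or changes the denominator.

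**2. Which rows are affected?** Week 64 falls (64 - 52) x 7 = 84 days after Week 52. The on-therapy window in SAP 11.3.2.3 closes 56 days after the last dose. For subjects who complete treatment, Week 64 values are therefore outside the any-on-therapy row. The any-post-baseline row is not limited to retested subjects. The problem sits in the by-visit Week 64 rows.

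**3. Size if only the abnormal test is repeated.** Assumptions: a standard normal analyte, abnormal above a cut-off c; the same true abnormal share p at both visits; Week 52 to Week 64 correlation r.

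Displayed rate = P(abnormal at both visits) / p.

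| True rate p | r = 0.3 | r = 0.5 | r = 0.7 |
|---|---|---|---|
| 5% | 14.3% | 24.4% | 39.2% |
| 10% | 21.6% | 32.4% | 46.8% |
| 20% | 33.1% | 43.6% | 56.5% |

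Expected number retested, from the planned arm sizes: 51 x 0.05 to 51 x 0.20 = 2.6 to 10.2 on albiglutide, and 17 x 0.05 to 17 x 0.20 = 0.9 to 3.4 on placebo.

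**4. Size if the whole panel is repeated.** Let q be the assumed chance that some other analyte triggers the repeat, independently of this one.

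Share tested = p + (1 - p)q. Displayed rate = [P(both) + (p - P(both))q] / share tested.

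For p = 0.10 and r = 0.5, P(both) = 0.324 x 0.10 = 0.0324. At q = 0.3, the share tested is 0.10 + 0.90 x 0.3 = 0.37, and the displayed rate is (0.0324 + 0.0676 x 0.3) / 0.37 = 14.2%.

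| True rate p (r = 0.5) | q = 0.3 | q = 0.6 | q = 0.9 |
|---|---|---|---|
| 5% | 7.0% | 5.6% | 5.1% |
| 10% | 14.2% | 11.4% | 10.2% |
| 20% | 27.5% | 22.8% | 20.5% |

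**5. Means.** With only the abnormal test repeated, the Week 64 level among those tested is shifted by r x phi(c) / p, where phi is the normal density. At p = 0.10 this is 0.53, 0.88 and 1.23 SD for r = 0.3, 0.5 and 0.7. The tables show change from baseline, and baseline is selected too if it correlates with Week 52. Subtracting its shift gives, for example, 0.88 - 0.53 = 0.35 SD with r = 0.5 and a baseline to Week 52 correlation of 0.3. It gives zero if the two correlations are equal. With a panel repeat at p = 0.10 and r = 0.5, the level shift is 0.17 SD at q = 0.3 and 0.01 SD at q = 0.9.

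**The case against.** The strongest reply is that the distortion may be negligible. Footnote 18 is attached to panel rows, not to individual analytes, so a panel repeat is the more natural reading. Most retested subjects would then have been abnormal on something else. Glucose is in the chemistry and urinalysis panels and is a plausible trigger in this population, though how often is unknown. This stands, and it is why the size is given as a range that reaches almost nil.

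Abnormal also need not mean PCI. SAP 11.7.1 sets separate limits, such as ALT at or above twice the upper limit of normal. A subject retested for a value just outside the normal range could be PCI-normal at both visits. A reader might therefore infer a certain jump in the PCI percentage at Week 64; the documents do not support that.

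Two other strong readings fail:
- That this is the trial's only off-drug laboratory display. Immunogenicity is sampled unconditionally at Week 64 and tabulated by visit and phase, and the any-post-baseline PCI row and the maximum post-baseline liver plots also take in Week 64 values.
- That a treatment comparison is compromised. Protocol 8.3.5.4 rules out inferential testing of safety variables.

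Dividing the Week 64 abnormal count by the whole arm is no remedy. It counts untested subjects as normal and gives only a lower bound.

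Finally, Listing 73 already gives all laboratory data for any subject with a PCI value, and the visits displayed may depend on standard table shells that are not in the documents. The listing helps those subjects but does not correct a summary row. Unseen shells cannot be relied on for an exemption that the SAP never states.

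**Conclusion.** The point holds as a minor one. As written, the SAP produces Week 64 rows for a subset chosen for an earlier abnormality, and those rows are not comparable with Week 52.

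The size cannot be fixed from the documents. For an assumed true rate of 10%, it runs from a displayed 22-47% (single-test repeat, correlation 0.3-0.7) down to 10-14% (panel repeat, correlation 0.5, q from 0.9 to 0.3). These figures rest on a normal model, a stable true rate, a one-sided definition of abnormal that matches the one tabulated, and independent triggers.

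The effect is confined to descriptive tables at the only scheduled post-treatment time-point for these tests in subjects who complete treatment. The primary analysis is untouched, and HbA1c and the mixed meal test at Week 64 are not conditional.

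**What to change.** In SAP 8.2.2.1 and 11.5.3:
- Leave Week 64 out of the by-visit rows of Tables 3.45 to 3.50.
- Show paired Week 52 and Week 64 values for the retested subjects, by arm, with the number abnormal at Week 52, the number retested and the number resolved. Note that some resolution is expected from regression to the mean.
- State the definition of abnormal that was used, and whether the single test or the whole panel was repeated. Without this the number resolved cannot be programmed.
- Keep Week 64 values in the any-post-baseline worst-case row.

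The cost is a short addition to the text and one small display, with no new data. The by-visit tables lose their Week 64 row. A footnote stating the selection would be the minimum alternative; it warns the reader but leaves the row in place.
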